6.2 Analysis of Endpoints

Primary Endpoints:

amount (mg) of narcotics (oral morphine mg equivalents) used
duration of narcotic use
patient reported pain scores

Secondary Endpoints:

length of stay
progress with physical therapy: distance ambulated, range of motion, exercises done
reported long-term narcotic use at home/SAR
discharge location: home, acute rehab, skilled nursing facility
documented narcotic refills
falls
adverse events

The analysis of narcotic Use, VAS, APS-POQ, and SMFA scores will rely on a univariate repeated-measures analysis of variance model for mean score. This model is in the class of models commonly known as a unirep-ANOVA models. It assumes that the mean score is a function of elapsed time and the treatment regimen assigned. This model takes into account the fact that the subject's repeated measures are correlated. The fitted model will provide statistical estimates of the mean levels, the treatment-effect differences between mean levels, the standard deviation, the intra-class correlation coefficient, 95% CIs, standard errors (SE), and statistical hypothesis tests. The estimates of means will be used to compute summary criteria such as area under the curve (AUC) for each regimen. All estimates reported will be presented their 95% CIs.

CONFIDENTIAL

This material is the property of the NYU School of Medicine and Langone Medical Center. Do not disclose or use except as authorized in writing by the study sponsor

Interventional Template Version: 28 APR 2017

All endpoints will be evaluated as fits the data set with graphical figures such as scatter plots, box-and-whisker plots, and frequency histograms to visualize the distribution of these outcomes and their relationships to covariates and treatment assignment. When appropriate descriptive graphical and tabular methods, and Kaplan-Meier curves will also be estimated and presented in a graphical figure.

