SAE	Serious adverse event
IV	Intravenous
PO	Taken orally
PRN	Taken as needed
TID	Taken three times per day
Q4h	Taken every four hours
CI	Confidence interval
SD	Standard deviation; a parameter which characterizes a population distribution
SE	Standard error
SSI	Surgical Site Injection
ANOVA	analysis of variance; a linear model
NSAID	Non-steroidal anti-inflammatory drug
LOS	Length of Stay

CONFIDENTIAL

This material is the property of the NYU School of Medicine and Langone Medical Center. Do not disclose or use except as authorized in writing by the study sponsor
Interventional Template Version: 28 APR 2017

Protocol Summary

Title	Effects of a Surgical Site Injection on Pain Scores and Narcotic Use after Orthopedic Trauma Surgery
Short Title	Understanding and Improving post-operative Pain in the Fracture Population
Brief Summary	This is a phase I, randomized, single-blind, placebo-controlled, single-center study of the effects of surgical site injection on pain and narcotic utilization in participants who undergo surgery for lower extremity fractures. 400 participants with lower extremity fractures who are admitted for operative fixation will be included in the study. Participants will be randomized to receive either a pain cocktail injection around the fracture site and surrounding tissues or control (no injection). An analysis of pain scores, rehabilitation progress, length of stay, narcotic utilization, and satisfaction scores will be performed.
Phase	Clinical study phase 1
Objectives	To understand the effect of surgical site injections of post-operative pain control
Methodology	phase I, randomized, single-blind, placebo-controlled, single-center study
Endpoint	10mg change in narcotic utilization daily or 15mm change in VAS
Study Duration	4 years
Participant Duration	3 months
Duration of IP administration	Once during surgery
Population	400 participants with peritrochanteric fractures
Study Sites	NYU Langone (Kimmel, Tisch, Langone Orthopedic Hospital, Lutheran)
Number of participants	400
Description of Study Agent/Procedure	Peri-incisional injection of 40cc 0.25% bupivacaine, 5 mg morphine sulfate (1 mg/cc, 5 cc total), and 30 mg of ketorolac (30 mg/cc, 1 cc total) into soft tissue and musculature surrounding the fracture site and 0.25% Marcaine 10 mL into the subcutaneous tissue surrounding the surgical incision.
Reference Therapy	Reference is a control
Key Procedures	Surgical Site injection

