Statistical Analysis	As treated analysis will be performed with mean, t-tests, within and between group ANOVA, linear regression, Mann- Whitney-Wilcoxon tests

CONFIDENTIAL

This material is the property of the NYU School of Medicine and Langone Medical Center. Do not disclose or use except as authorized in writing by the study sponsor
Interventional Template Version: 28 APR 2017

1 Key Roles

PI: [name]
Department of Orthopedic Surgery and Cell Biology
NYU Langone Medical Center
[name]
[contact]
[contact]

Co-PI:

[name]
Assistant Professor of Anesthesiology
NYU Langone Orthopedic Hospital
NYU Langone Health
[name]
[name]
[contact]

2 Background and Specific Aims

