2.3 Statistical Hypotheses

We hypothesize that SSI given at the time of surgery will reduce post-operative pain and narcotic usage not only during the patients' inpatient hospital stay but also as an outpatient. Furthermore, SSI will improve post-operative function, shorten length, of stay, and reduce complications not limited to but including deep venous thrombosis, delirium, and narcotic dependency. Failing to reject the null hypothesis would signify that SSI has no clinically relevant impact on post-operative outcomes in hip fracture surgery.

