2.4 Objectives and Purpose

The ultimate goal of this study is to determine how effective SSI is in reducing post-operative pain in patients with lower extremity long bone fractures and to determine how that reduction in post-operative pain impacts a patient's hospital stay in the short term and their use of narcotics during the treatment period. Primary outcomes measures will be reported and observed pain scores and narcotic use. VAS and APS-POQ will be used to measure pain scores. While it is expected that the greatest benefit of the SSI will be seen in the first day or two after surgery it is possible that there will be an overall reduction in long-term narcotic use. Secondarily, function/rehabilitation, length of stay, and complications may be impacted by the intervention.

CONFIDENTIAL

This material is the property of the NYU School of Medicine and Langone Medical Center. Do not disclose or use except as authorized in writing by the study sponsor

Interventional Template Version: 28 APR 2017

3 Study Design and Endpoints

Cohort A: Spinal Anesthesia	ARM 1: Experimental	Sample Size: 100	SSI
	ARM 2: Control	Sample Size: 100	No intervention

Cohort B: General Anesthesia	ARM 1: Experimental	Sample Size: 100	SSI
	ARM 2: Control	Sample Size: 100	No intervention

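### Three unranked primary endpoints, with no rule for family-wise error and no fixed window or pain instrument; secondarily, an efficacy stop with no boundary

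*Combined protocol and SAP*

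**What the plan says.** Section 6.2 of the combined protocol and SAP gives three primary endpoints: "amount (mg) of narcotics (oral morphine mg equivalents) used", how long narcotics are used, and pain as the patient reports it. It gives no order, co-primary rule or split of alpha.

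Two other places describe the primary outcome differently. Section 2.4 states "Primary outcomes measures will be reported and observed pain scores and narcotic use" and adds "VAS and APS-POQ will be used to measure pain scores". The Endpoint row of the Protocol Summary reads "10mg change in narcotic utilization daily or 15mm change in VAS".

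For analysis, 6.2 assigns narcotic use, VAS, APS-POQ and SMFA to a repeated-measures ANOVA: "It assumes that the mean score is a function of elapsed time and the treatment regimen assigned". Its outputs include treatment differences in means and "the intra-class correlation coefficient, 95% CIs, standard errors (SE), and statistical hypothesis tests". AUC appears as an example of a summary measure. Kaplan-Meier curves are mentioned for use where suitable but are not tied to an endpoint. Section 6.1 demotes methods outside the main analyses to a supporting role.

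Alpha of 0.05 appears only in 6.3, once for the study and once for the test of morphine-equivalent consumption. Sidedness is not stated. The hypothesis in 2.3 is directional ("SSI given at the time of surgery will reduce post-operative pain and narcotic usage"), while Aim 2 in 2.2 speaks only of a change.

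Section 4.8, item 2, allows the study to stop if injected patients need markedly less oral narcotic than controls. It gives no threshold, number of looks or alpha spent.

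**The concern.** When any one of several primaries can carry the claim, testing each at 0.05 does not hold the study at 0.05. The either/or in the Summary points to that structure.

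The freedom also extends inside each endpoint. Under 3.1, VAS is recorded every four hours in hospital, and pain and narcotic use are asked again at repeated calls after discharge. Pain has two instruments and no primary window is named. Duration of narcotic use has no assigned test. The window, the instrument and the duration test could therefore all be settled after the data are seen, and a chance result reported as the primary finding.

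The 4.8 item is a separate and smaller matter. If the arms were compared during the trial and it were stopped on an apparent narcotic benefit, the narcotic test would no longer hold 0.05, and the estimate at stopping would tend to be too large.

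**Working it through.** **Inputs.** From 6.3: alpha 0.05, power 0.80, difference 15 mg/day, SD 25 mg. From the Summary: 10 mg/day. From 4.6: 300-350 evaluable, so 150-175 per arm pooled and, with equal cohorts, 75-87.5 per arm in each. Assumed: two-sided tests, each primary tested once on pooled cohorts, equal pairwise correlation between endpoints of 0 to 0.9, and one half-way look for the 4.8 illustration.

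**1. The plan's own figure.** n per arm = 2(1.960 + 0.842)² × 25²/15² = 43.6, so 44; the t-test gives 44.6, so 45. The stated 90 is therefore both arms of one anaesthesia cohort (2 × 45). As 90 per arm, power would be 98%. The calculation spends the whole 0.05 on one narcotic test and leaves nothing for the other primaries.

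**2. Chance of at least one false positive.** With independent endpoints, 1 − 0.95² = 9.75% and 1 − 0.95³ = 14.3%. With correlation, by simulation:

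| Correlation | Two primaries | Three primaries |
|---|---|---|
| 0 | 9.75% | 14.3% |
| 0.5 | 9.1% | 12.5% |
| 0.7 | 8.4% | 10.9% |
| 0.9 | 7.0% | 8.4% |

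In the favourable direction only (nominal 2.5%), independence gives 1 − 0.975² = 4.9% and 1 − 0.975³ = 7.3%. Correlation 0.9 gives 3.5% and 4.2%.

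**3. With Holm.** If all three nulls are true, Holm rejects something only when the smallest p is below 0.05/3 = 0.0167. Independent: 1 − (1 − 0.0167)³ = 4.9%. Correlation 0.9: 3.0%.

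**4. The 4.8 stop, if used.** Take one look at half the information (correlation of look and final statistic √0.5 = 0.71), stopping only if Z > 1.96 in favour of the injection, then a two-sided final test. Benefit side: P(Z₁ > 1.96 or Z₂ > 1.96) = 4.2%. Adding the 2.5% lower tail of the final test gives 6.7%. With the look at p < 0.001 instead, the overall error is about 5.0%.

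**5. Power cost.** Two-sample t-test, noncentrality (difference/25) × √(n per arm/2). For example, 10 mg with 150 per arm gives 0.4 × √75 = 3.46, against normal critical values of 1.96 and 2.39.

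| Analysis | Difference | n per arm | Power at 0.05 | Power at 0.0167 |
|---|---|---|---|---|
| Pooled | 10 mg | 150-175 | 93-96% | 85-91% |
| Within one cohort | 10 mg | 75-87.5 | 68-75% | 51-59% |
| Within one cohort | 15 mg | 75-87.5 | 96-98% | 89-94% |

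These figures carry the SD of 25 mg to whatever window is chosen; 6.3 ties that SD to none. Power for VAS and duration cannot be computed, because the documents give no SD or event rate for them.

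**The case against.** Several points on the other side stand.

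- **Choice of test.** The Summary lists "mean, t-tests, within and between group ANOVA, linear regression" and rank tests, and a reader might infer an open menu for every primary. Sections 6.1 and 6.2 do not support that. Narcotic use and pain have one main method, the repeated-measures ANOVA, and competing methods are only supportive. The choice is open for duration alone.
- **Contrast.** A reader might infer that treatment-by-time tests add further chances of a primary claim. Section 6.2 mentions no such interaction and does name treatment differences in means. What is missing is the window.
- **Window.** Aim 2 places narcotic measurement in the immediate post-operative period and over two weeks, and 6.2 makes long-term narcotic use secondary. That narrows the choice but designates no single window.
- **Size.** Amount and duration of narcotic use are linked, so independence, and with it 14%, is unlikely. Even at correlation 0.9 the figure is 8.4%.
- **Lead endpoint.** Section 6.3 sizes on morphine equivalents, which suggests a lead endpoint. Sizing on an endpoint does not rank it, and 6.2 lists all three equally.
- **Interim looks.** A reader might take the weekly review in 7.4, together with 4.8, for repeated efficacy testing. The stated purpose of that review is data quality and safety, and no interim analysis is scheduled. Nor does the usual 8.3% for one unadjusted two-sided look apply: it counts stops for harm, and 4.8 item 2 covers benefit only.

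**Conclusion.** The main point holds: the primaries are unranked and no rule controls error across them. Under unadjusted two-sided 0.05 tests, the family-wise error is 8-14% for the three primaries in 6.2 and 7-10% for the two in 2.4 and the Summary. The lower part of each range is the more credible. On the directional reading of 2.3, the figures are 4.2-7.3% and 3.5-4.9%, against 2.5%. The correlations, the sidedness and one test per primary are assumptions, since the documents give none of them.

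The undefined window, the two pain instruments and the missing test for duration also hold; an error rule across endpoints needs these settled to be meaningful.

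The 4.8 point is conditional and of lower priority: 6.7% overall (4.2% on the benefit side) for one unadjusted half-way look, and no inflation if the arms are never compared early. The documents do not show that such looks are planned.

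**What to change.** **Main change, in 6.2.** Name one instrument, one window and one treatment-effect test for each primary. Control two-sided 0.05 across them by Holm, or by a fixed order stated in advance, for example morphine-equivalent amount first because 6.3 sizes on it. Suitable definitions are:

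- narcotic amount over a single window chosen to agree with Aim 2;
- VAS over the first 48 hours, since 2.4 expects the greatest benefit in the first day or two;
- duration by a log-rank test stratified by anaesthesia group.

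Make the other pain instrument, other windows and cohort-specific tests secondary. State whether the confirmatory test is pooled and stratified by anaesthesia group, which is how 6.4 randomises, or made within each cohort. Bring 2.4 and the Summary into line.

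**Lower priority, in 4.8 and 7.4.** Remove the efficacy item, or tie it to one pre-specified look at p < 0.001 and name who performs it. State in 7.4 that the weekly review makes no between-arm efficacy comparison.

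**Cost.** An IRB-approved amendment, no extra patients, and the loss of power in the second table. That loss is modest when pooled. Within one cohort at 10 mg/day it leaves 51-59%, which the sponsor should weigh when choosing between pooled and within-cohort testing. A fixed order with narcotic amount first costs that test no power; the later endpoints then depend on it succeeding.

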Physical therapy records with regards to ambulation distance and exercise endurance will be examined. Daily assessments of pain via VAS will be obtained by the nursing staff as per standard protocol. APS-POQ form will be given on POD1.

After discharge subjects will receive a 7-10 day prescription for acetaminophen 1000mg every 8 hours, meloxicam 15mg oral once daily, and tramadol 50mg oral, every 4-6 hours, PRN (12 tablets to be dispensed). Subjects will call the provider to request refills as needed.

CONFIDENTIAL

This material is the property of the NYU School of Medicine and Langone Medical Center. Do not disclose or use except as authorized in writing by the study sponsor

Interventional Template Version: 28 APR 2017

[figure not shown]
After discharge the research staff will call the subjects up to every other day for the first week, twice in the second week, once weekly for the third and 4th weeks and then monthly after discharge to ascertain pain level, reported narcotic usage, and functional status. Research staff will verify documented narcotic refills through epic and pharmacy records. Four to eight weeks after injury subjects will complete a SMFA as well as another APS-POQ form over the phone with a trained interviewer.

	Pre-op	Post-op: Inpatient	Post-op: Discharge
Standing	Acetaminophen 1gm, oral (every 6-8 hours, not to exceed 4gm daily, review liver function prior to administration)	Acetaminophen 1gm, oral (every 6-8 hours, not to exceed 4gm daily, review liver function prior to administration)	Acetaminophen 1gm, oral (every 6-8 hours, not to exceed 4gm daily, review liver function prior to administration)
	Meloxicam 15mg oral, once daily	Ketorolac 30mg inj, once daily in AM, starting POD1 (15mg>65 years of age and/or renal impairment) Pregabalin (Lyrica) 50mg, oral every 8 hours (hold for sedation)	Meloxicam 15mg oral, once daily
Mild		Ice Therapy PRN (alternating 15 min on/off for skin evaluation)	
Moderate		Tramadol 50mg oral, every 8 hours, PRN	
Severe		Tramadol 100mg, oral, every 8 hours, PRN	
Breakthrough		Oxycodone 5mg, oral every 6 hours, PRN	Tramadol 50mg oral, every 4-6 hours, PRN (12 tablets to be dispensed)

CONFIDENTIAL

This material is the property of the NYU School of Medicine and Langone Medical Center. Do not disclose or use except as authorized in writing by the study sponsor
Interventional Template Version: 28 APR 2017

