4.6 Total Number of Participants and Sites

Recruitment will end when approximately 400 participants are enrolled. It is expected that approximately 400 participants will be enrolled in order to produce 300-350 evaluable participants. There were 350 procedures done on patients matching the inclusion and exclusion criteria in the last year. Based on the simplicity of the intervention and historical enrollment for patients undergoing orthopedic surgery, we anticipate at least 25% participation.

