6.1 General Approach

As treated Sample. The primary analyses will follow the as-treated principle in order to evaluate the true outcome of the intervention as experienced by the patient who is blinded to the intervention.

Missing Data. It is anticipated that the data for some subjects will be incomplete for various reasons: missed clinic visits, refusal to answer a sensitive question on a questionnaire, onset of illness, loss-to-follow-up, etc. All occurrences of incomplete data will be investigated to carefully document the reasons for the missing data.

Sensitivity Analyses. To evaluate the robustness of the main results to reasonable perturbations of the methods and assumptions used, competing statistical methods (those not used in the main analyses) will be relegated to serving as a guide to our confidence in the main results.

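### Duration of narcotic use is a primary endpoint with no window, censoring rule or time-to-event test, so patients without a stop date can bias the arm comparison

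*Combined protocol and SAP*

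**What the plan says.** Section 6.2 lists "duration of narcotic use" among the primary endpoints, beside the amount of narcotics and reported pain scores. It does not say when the duration starts, what counts as stopping, or over what period it is measured.

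The inferential model in 6.2 is: "The analysis of narcotic Use, VAS, APS-POQ, and SMFA scores will rely on a univariate repeated-measures analysis of variance model for mean score". Duration is not named separately. The Protocol Summary adds a general list that is not tied to endpoints: "As treated analysis will be performed with mean, t-tests, within and between group ANOVA, linear regression, Mann- Whitney-Wilcoxon tests". The one time-to-event method is descriptive. Where appropriate, "Kaplan-Meier curves will also be estimated and presented in a graphical figure", for no named endpoint and with no test.

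On incomplete data, section 6.1 says: "All occurrences of incomplete data will be investigated to carefully document the reasons for the missing data". It gives no rule for exclusion, imputation or censoring. Section 4.6 expects that "approximately 400 participants will be enrolled in order to produce 300-350 evaluable participants", and section 6.3 anticipates poor follow-up. After the first week, section 3.1 schedules calls "twice in the second week, once weekly for the third and 4th weeks and then monthly after discharge".

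The documents point to different windows. Aim 2 in section 2.2 measures narcotic use in hospital and for 2 weeks after surgery. The Protocol Summary gives 3 months of participation, and the calls in section 3.1 ask about narcotic use monthly after week 4. Section 6.2 also lists long-term use at home as a separate secondary endpoint, which leaves the period of the primary endpoint more open still.

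**The concern.** Duration is one time-to-stop value per patient. A repeated-measures model of a mean score over elapsed time has no natural place for it. The t-test, linear regression and Mann-Whitney test accept it only if every analysed patient has been given a value. Two kinds of patient have no observed stop: those lost to the calls while still using, and those still using when the window closes. Both are more likely to be long users, and there are more of them in the arm with longer use.

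The plan leaves open whether these patients are omitted, given their last contact as the stop date, or censored. The three choices can give different answers on a primary endpoint, and nothing prevents the choice being made after the data are seen. The gaps between calls, which grow to about a month, add a second error: a stop reported at a call may be recorded up to a month late.

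**Working it through.** The plan states no effect size, SD or sample size for duration. The figures in section 6.3 (15 mg daily, SD 25 mg, 90 per group) concern the amount of narcotics, so there is nothing on duration to reproduce.

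**Inputs from the documents.** Loss: 1 − 350/400 = 12.5% to 1 − 300/400 = 25% (section 4.6). Windows: 14 days (Aim 2) or about 90 days (3 months, Protocol Summary).

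**Assumptions, none of them in the documents.** Exponential durations with the means shown; for the 90-day window, loss at random and uniform over days 4-90, and calls on days 4, 6, 8, 11, 14, 21, 28, 60 and 90. Other reasonable call days move the results by about 0.1 day.

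**Step 1: true target.** For mean m and window W, the restricted mean is m(1 − exp(−W/m)).
- 45 v 30, W = 90: 45(1 − e^−2) − 30(1 − e^−3) = 38.9 − 28.5 = 10.4 days
- 20 v 15, W = 90: 19.78 − 14.96 = 4.8 days
- 14 v 10, W = 14: 14(1 − e^−1) − 10(1 − e^−1.4) = 8.85 − 7.53 = 1.3 days

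**Step 2: only patients who stop within the window, exact dates, no loss.** The mean among them is m − W·exp(−W/m)/(1 − exp(−W/m)).
- 45 v 30, W = 90: 30.9 − 25.3 = 5.6 days
- 20 v 15, W = 90: 18.99 − 14.78 = 4.2 days
- 14 v 10, W = 14: 5.85 − 5.42 = 0.4 days, leaving out e^−1 = 37% of controls and e^−1.4 = 25% of SSI

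**Step 3: 90-day simulation with 12.5-25% loss.**

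| Difference in days | Means 45 v 30 | Means 20 v 15 |
|---|---|---|
| True, restricted to 90 days | 10.4 | 4.8 |
| Stop-date cases only, exact dates | 5.3-5.5 | 3.8-4.0 |
| Stop-date cases only, stop rounded up to the next call | 6.5-6.8 | 5.0-5.3 |

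For 45 v 30, taking last contact as the stop date gives 8.8-9.6, and stop-date cases omit 18-23% of controls and 9-13% of SSI. A Kaplan-Meier restricted mean, with the stop date asked and censoring at the last call, returns the true difference to within about 0.1 day.

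The two error sources separate here. Omission alone shrinks the difference in both columns. Rounding to call dates pushes it back up, and in the 20 v 15 case past the true value.

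**Step 4: direction when the effect is not spread evenly (90 days, no loss).**
- 15% persistent users in each arm, SSI acting only on the rest (14 v 10): true difference 0.85 × (13.98 − 10.00) = 3.4 days; stop-date cases 13.85 − 9.99 = 3.9 days. The difference grows.
- SSI acting only on persistence (15% v 8%), mean 12 days in the rest: true difference 0.07 × (90 − 12.0) = 5.5 days; stop-date cases about 0. The effect vanishes.

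**Step 5: power (200 v 200, means 14 v 10, 25% loss uniform over the window).**

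| Window | t-test, stop-date cases | t-test, last contact as stop | Log-rank, censored |
|---|---|---|---|
| 14 days | 0.13 | 0.62 | 0.76 |
| 90 days | 0.89 | 0.90 | 0.91 |

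**The case against.** A reader might infer that the plan discards every patient without a stop date, so that the longest users drop out and the arm difference must shrink. The documents do not support this. No exclusion is written, section 6.1 only records reasons for incomplete data, and no listed test is assigned to duration. Step 4 also shows that omission can enlarge the difference.

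The listed tests can be used sensibly. A patient still using at day 90 can be entered at 90, and Mann-Whitney would rank such patients as tied longest. For 45 v 30, capping at day 90 among patients followed to day 90 gives about 10.4 days, essentially the true value under random loss. Entering last contact as the stop date is off by 8-15% (8.8-9.6 against 10.4), far less than omission.

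Means of 45 and 30 days may be long for this population: prior or current narcotic use is excluded (section 4.2), and 12 tramadol tablets are dispensed at discharge, with refills on request (section 3.1). Refills are checked in Epic and pharmacy records, and section 6.1 promises sensitivity analyses by competing methods.

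Much of this stands. It rules out any single percentage for the bias and any fixed direction. It does not close the gap. The capping rule that would work is not in the plan, and it sets aside the 12.5-25% who are lost. Refill records give only partial information on when use stopped. The sensitivity paragraph names no method for censored durations.

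**Conclusion.** The point holds in a limited form. A primary endpoint that is a time to an event has no window, no censoring rule and no test that accommodates censoring, in a trial that itself expects poor follow-up. The consequence is possible bias in the arm comparison, usually but not always toward no effect.

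Its size is conditional. Over 90 days it ranges from roughly half the true difference (5.3-5.5 of 10.4 days, long durations, stop-date cases with exact dates) to a slight overstatement (5.0-5.3 against 4.8, shorter durations, call-date rounding). Over the 2-week window of Aim 2, stop-date cases retain about a third of the true restricted difference (0.4 of 1.3 days). All of these figures rest on assumed exponential durations, and those with loss also on random loss. They show that the unstated rule and window matter; they do not predict this trial's result.

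**What to change.** In section 6.2:

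1. Fix one window for the primary duration endpoint, reconciling the 2 weeks in Aim 2 with the 3 months of participation and the monthly calls, and align the secondary endpoint on long-term use with it.
2. Define duration as time from surgery to the last opioid dose, right-censored at the last completed contact or the end of the window, with death as a competing event.
3. Test it with a log-rank test stratified by anaesthesia type (spinal or general), matching the randomization. Report the difference in restricted mean time to the fixed day with its 95% CI.
4. State that the ANOVA, t-test, linear regression and Mann-Whitney methods are not the primary analysis of duration.

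At each call already scheduled in section 3.1, ask the date of the last opioid dose, so that stop times are not rounded to call dates.

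The cost is a few sentences of analysis text and one question on the call form. No patients, visits or treatments are added.
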